7.5. Missed Visits

Every attempt should be made to complete all study visits within the visit window as outlined in the Schedule of Assessments.

7.6. Unscheduled Visits

Unscheduled visit(s) and laboratory assessments may be required at the discretion of the investigator. Please refer to the eCRF completion guidelines for additional information.

7.7. Laboratory Assessments

Details regarding sample collection, preparation and transport can be found in the central laboratory manual. Importantly, dose adjustments per the dosing algorithm will be made on results from local Hb testing.

7.8. Central Laboratory

The following labs will be evaluated by a central laboratory in accordance with the SOA in Table 4.

Protocol FGCL-4592-096 A01

Roxadust at

Table 5: Central Laboratory Tests

CBC:	Chemistry Panel:
Basophils	Albumin
Eosinophils	Bicarbonate
Erythrocyte count (RBC)	BUN
Hct	Calcium
НЬ	Chloride
Leukocyte count (WBC)	Creatinine
Lymphocytes	Creatine phosphokinase
Mean corpuscular volume	Glucose
Mean corpuscular Hb	Lactic Acid Dehydrogenase
Mean corpuscular Hb concentration	Liver Function Tests ¹
Monocytes	ALP
Neutrophils	ALT
Neutrophils, immature (banded)	AST
Platelets	Bilirubin, total and direct
Serum Iron Profile:	GGT
Ferritin	Magnesium
Iron	Phosphorus
TIBC	Potassium
UIBC	Total protein
TSAT	HIV and viral Hepatitis Panel:
Additional Laboratory Analytes:	Anti-HCV Ab tests
Reticulocyte count	HBsAg
CHr	HIV ELISA
Serum hCG pregnancy test (for women of childbearing potential only)	

Abbreviations:

ALP = alkaline phosphatase; ALT = alanine aminotransferase; AST = aspartate aminotransferase; BUN = blood urea nitrogen; CBC = complete blood count; CHr = reticulocyte hemoglobin content; ELISA = enzyme-linked immunosorbent assay; GGT = gamma-glutamyl transferase; Hb = hemoglobin;; HBsAg = hepatitis B surface antigen; Hct = hematocrit; HCV = hepatitis C virus;; HIV = human immunodeficiency virus; RBC = red blood cell; TIBC = total iron binding capacity; UIBC = unsaturated iron binding capacity; TSAT = transferrin saturation; WBC = white blood cell.

In case a patient shows an AST or ALT \geq 3xULN and total bilirubin \geq 2xULN, please refer to Appendix 2 "Liver Function Monitoring".

8. SAFETY

8.1. Background

Subjects will be asked for the occurrence of potential AEs during each study visit. In addition, all AEs reported spontaneously during the course of the study will be recorded. The Investigator must immediately (within 24 hours of becoming aware) report to the sponsor all SAEs, regardless of whether the Investigator believes they are related to the study drug.

The definitions of an AE, suspected adverse reaction, adverse reaction, and SAE are described below in accordance with the FDA Final Rule Vol 75, No 188, September 29, 2010; Article 18 of Directive 2001/20/EC of the European Parliament and of the Council of 4 April 2001and the ICH E2A guidance.

8.2. **Definitions**

8.2.1. Definition of an Adverse Event

An AE is any untoward medical occurrence associated with the use of a drug in humans, whether or not considered drug-related.

An AE can be any unfavorable and unintended sign (e. g., an abnormal and clinically significant laboratory finding), symptom, or disease temporally associated with the use of a drug, without any judgment about causality. This includes any occurrence that is new in onset or aggravated in severity or frequency from the BL condition, or abnormal results of diagnostic procedures, including laboratory test abnormalities. An AE can arise from any use of the drug (e.g., off-label use, use in combination with another drug) and from any route of administration, formulation, or dose, including an overdose.

An AE includes medical conditions, signs, and symptoms not previously observed in the subject that emerge during the protocol-specified AE reporting period, including signs or symptoms associated with an underlying condition that were not present prior to the AE reporting period (Section 8.3.1)

8.2.2. Definition of a Serious Adverse Event

An **SAE** is any AE or suspected adverse reaction that results in any of the following outcomes:

- Death
- A life-threatening AE (i.e., if in the view of the Investigator or sponsor, the subject was at immediate risk of death at the time of the event). Life-threatening does not refer to an event which hypothetically might have caused death if it were more severe.
- Inpatient hospitalization or prolongation of existing hospitalization
- A persistent or significant incapacity or substantial disruption of the ability to conduct normal life functions
- A congenital anomaly or birth defect
- A medically important event not meeting the above criteria, but which may jeopardize a patient or may require medical or surgical intervention to prevent one of the other criteria listed in this definition. Examples of such medical events include allergic bronchospasm

requiring intensive treatment in an emergency room or at home, and blood dyscrasias or convulsions that do not result in inpatient hospitalization

8.3. Procedures for Eliciting, Recording, and Reporting Adverse Events

8.3.1. Adverse Event Reporting Period

The study period during which all AEs and SAEs must be reported begins after informed consent is obtained and ends 28 days after the last study visit, except for pregnancy reporting (Section 8.3.6). AEs (non-SAE) reported during screening should be reviewed and captured under medical history, if applicable.

Adverse events will be followed until resolved, stable, or until the subject's last study visit or lost to follow-up. If an AE is not resolved or stabilized at the subject's last visit, it is up to the discretion of the investigator and/or study Medical Monitor to determine if further monitoring of the event is warranted.

Adverse events collected prior to dosing of study drug will be considered "non-treatment emergent" while those reported after the first dose of study drug and up to 28 days after the last dose of study drug will be considered "treatment emergent" and be assessed for relationship to study drug. If an AE starts on Day 1, the investigator must assess as to whether the AE started prior to or after the administration of study medication and record accordingly.

8.3.2. Adverse Event Eliciting/Reporting

During the AE reporting period, study site personnel will query each subject/caregiver at each visit to assess for any AEs occurring since the previous visit. All AEs will be collected in response to non-leading, general questions about the subject's well-being and any possible changes from the baseline or previous visit. This does not preclude the site from collecting and recording any AEs reported by the subject/caregiver to site personnel at any other time.

Whenever possible, AE diagnoses should be recorded rather than just the signs and symptoms, as determined by qualified medical study staff. New indications for medications started after informed consent is obtained until 28 days after the last dose of study drug will be recorded as AEs; recurrence or worsening of medical conditions will also be recorded as AEs. Abnormal, clinically significant laboratory results, and PE findings will be recorded as AEs if they are deemed by the Investigator to meet the AE criteria.

The following attributes must be assigned to each AE:

- Description (Investigator's verbatim term describing the event).
- Dates of onset and resolution
- Severity
- Relationship to study drug
- Outcome
- Action taken regarding study drug (action taken by the PI in response to an AE)
- Other treatment required
- Determination of "seriousness"

8.3.3. Assessing Adverse Event Severity

The Investigator should use the National Cancer Institute (NCI) Common Terminology Criteria for Adverse Events (CTCAE) version 4.0. For terms not specified as part of NCI-CTCAE, the following guidelines should be used to determine grade:

- **Grade 1, Mild**: Asymptomatic or mild symptoms which the subject finds easily tolerated. The event is of little concern to the subject and/or of little-or-no clinical significance; clinical or diagnostic observations only; intervention not indicated.
- **Grade 2, Moderate:** The subject has enough discomfort to cause interference with or change in some of their age-appropriate instrumental activities of daily living (e.g., preparing meals, shopping for groceries or clothes, using the telephone, managing money); local or noninvasive intervention indicated.
- **Grade 3, Severe:** The subject is incapacitated and unable to work or participate in many or all usual activities. The event is of definite concern to the subject and/or poses substantial risk to the subject's health or well-being; Likely to require medical intervention and/or close follow-up, including but not limited to hospitalization or prolongation of hospitalization.
- **Grade 4, Life-threatening:** The subject was at immediate risk of death from the event as it occurred.
- Grade 5, Death related to AE.

8.3.4. Assessing Relationship to Study Drug

Most of the information about the safety of a drug prior to marketing comes from clinical trials; therefore, AE reports from Investigators are critically important. Moreover, appropriately deciding whether the AE meets the definition of a suspected adverse reaction is usually the most difficult determination, but it is critical to avoid the mis-categorization of the product's safety profile. Default reporting of individual events as possibly related is uninformative and does not meaningfully contribute to the development of the drug's safety profile.

The Investigator must provide an assessment of the relationship of the AE to study drug in accordance with the guidance below. Absence of an alternative cause would not normally be considered enough evidence to assess an event as possibly related or related to study drug. The following are examples of adverse events and their relationship to study drug:

Related (Adverse Reaction):

• Any event for which there is evidence to conclude that the study drug caused the event.

Possibly Related (Suspected Adverse Reaction):

- A single occurrence of an event that is uncommon, but is a typical drug toxicity and *known to be strongly associated with drug exposure*, such as anaphylaxis, rhabdomyolysis, Stevens-Johnson syndrome, etc.
- One or more occurrences of an event that is not commonly associated with drug exposure but is otherwise uncommon in the population exposed to the drug.

Not Related:

• The event represents the underlying disease (e.g., disease-related symptoms, disease progression) and the presentation of the event is typical.

- The event represents a comorbid condition present at the time the subject entered the study that has not worsened.
- The event represents a known adverse reaction associated with a co-medication received by the study subject.
- The event is common for the study population (e.g., cardiovascular events in an elderly population).

The Investigator must provide an assessment of the relationship of the event to study drug, as this information is very important to monitor the real-time safety of the study drug. However, as the manufacturer of the study drug, FibroGen is responsible for reporting suspected adverse reactions and adverse reactions to Health Authorities.

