4.7.1.3. Statins

When coadministered with roxadustat, in clinical pharmacolgical studies, hydroxymethylglutaryl coenzyme A reductase inhibitor (statin) exposure was increased 2- to 3-fold. Investigators should consider this interaction and local prescribing information when deciding on the appropriate statin dose for individual subjects, bearing in mind the impact of ethnicity, other concomitant medications, renal and hepatic function. Goals of lipid lowering treatment should be maintained as clinically indicated. The dose of statins should not exceed the recommended daily dose in Table 3.

Table 3: Recommended Maximum Daily Dose of Statins

Statins	Recommended maximum dose (mg/day)		
Atorvastatin	40		
Simvastatin	5		
Rosuvastatin	5		
Pravastatin	40		
Fluvastatin	20		
Pitavastatin	1		
Lovastatin	20		

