10.1.1 Proportion of Subjects with TEAE

An AE (classified by preferred term) started during the treatment period will be considered a TEAE if it was not present prior to the first dose of study medication, or it was present prior to the first dose of study medication but increased in severity during the treatment period. For subjects who permanently discontinue roxadustat early or complete the treatment period (24 weeks) but decide not to participate in the extension treatment, all AEs that occur up to 28 days after the last roxadustat dose will be counted as a TEAE. For subjects who complete the treatment period and decide to participate in the extension treatment, an AE that occurs after the treatment period (Week 24/EOT) will not be counted as a TEAE.

The number and percentage of subjects reporting TEAEs will be tabulated separately by system organ class and preferred term; by system organ class, preferred term, and severity; and by system organ class, preferred term, and relationship to study medication. If more than one event occurs with the same preferred term for the same patient, the patient will be counted only once for that preferred term using the most severe and most related occurrence for the summarization by severity and by relationship to the study medication.

The distribution of TEAEs by severity and relationship to study medication will be summarized.

The incidence of common ($\geq 5\%$ of subjects) TEAEs, common non-serious ($\geq 5\%$ of subjects) TEAEs (excluding TESAE), TESAEs, and AEs leading to discontinuation of study medication will be summarized by preferred term and sorted by decreasing frequency. In addition, the incidence of deaths and SAEs with a fatal outcome (i.e., events that caused death) will be summarized separately by preferred term.

AE summaries are presented as a crude incidence rate and patient exposure year (PEY) adjusted incidence rate. The PEY-adjusted incidence rate, per 100 patient exposure years, is defined as the incidence of an event divided by 100 times the PEY which is defined as (last dose date – first dose date +1) divided by 365.25.

Listings of subjects with SAEs, adverse events leading to discontinuation, and those who died will be presented

Temporal profile of TEAEs of special interest may also be plotted showing the subjects in the y-axis and time to these TEAEs in the x-axis ([Appendix 4](#)).

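### The causality guide's co-medication example under Not Related has no exception for drug interactions, so statin-type events to which roxadustat may have contributed can be under-attributed

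*Protocol*

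**What the plan says.** Protocol Section 8.3.4 sets out how relationship is rated: "The Investigator must provide an assessment of the relationship of the AE to study drug in accordance with the guidance below". The list that follows is introduced by "The following are examples of adverse events and their relationship to study drug" and has three categories.

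- **Related** covers "Any event for which there is evidence to conclude that the study drug caused the event".
- **Possibly Related** includes a single occurrence of an uncommon but typical drug toxicity, "such as anaphylaxis, rhabdomyolysis" and others.
- **Not Related** includes "The event represents a known adverse reaction associated with a co-medication received by the study subject".

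The last example is not qualified for interactions with study drug.

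Protocol Section 4.7.1.3 describes such an interaction. For coadministration with roxadustat it reports "statin) exposure was increased 2- to 3-fold", and it sets maximum statin doses in Table 3. Protocol Section 8.2.1 accepts that an adverse event can arise from "use in combination with another drug".

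SAP Section 10.1.1 tabulates TEAEs in several ways, one of which is "by system organ class, preferred term, and relationship to study medication". SAP Section 13.2.5 imputes a missing relationship as Related. Neither document has a rule that revisits a relationship entered as Not Related.

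**The concern.** The protocol tells investigators that roxadustat raises statin exposure, then gives them a causality example that takes no account of it. A CPK rise, myopathy, rhabdomyolysis or transaminase rise in a statin user can be read as a known reaction to the statin. If roxadustat contributed by raising statin exposure, Not Related is the wrong rating, yet the wording of the example leads there.

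Two outputs depend on this rating. One is the by-relationship TEAE tables. The other is the causal relationship that Protocol Section 8.3.5 requires as minimum information on every SAE report. The study has a single arm, so no control rate is available against which to judge an excess of muscle or liver events, and investigator attribution carries more weight than it would in a controlled trial. Confirming safe dosing is part of the primary objective (Protocol Section 3.1.1).

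**Working it through.** No sample size, interval or event count bears on this point, so the check sets the passages side by side.

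**1. Does the guide have force?** Yes. Investigators must rate in accordance with it (Section 8.3.4). Its entries are nevertheless headed as examples, so they steer judgement and do not form a complete decision rule.

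**2. How does it handle events in a statin user?**

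| Event | Related | Possibly Related | Not Related (co-medication example) |
|---|---|---|---|
| Rhabdomyolysis | Only with evidence that study drug caused it | Fits: named in the first example | Fits, read as a known statin reaction |
| Muscle pain or ordinary CPK rise | Only with such evidence | Poor fit: the first example concerns uncommon, typical drug toxicities; the second concerns events not commonly linked to drug exposure | Fits directly |
| ALT or AST rise | Only with such evidence | Poor fit, for the same reasons | Fits directly |

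For rhabdomyolysis, two examples give opposite answers and the section does not say which prevails. For the milder events, the co-medication example is the closest match.

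**3. Can the Related category rescue these events?** In principle yes, because its wording is not limited to direct effects. In practice the evidence is hard to obtain: neither the schedule in Protocol Table 4 nor the laboratory list in Table 5 includes a statin level. Section 8.3.4 also discourages rating events as possibly related by default, which adds to the pull towards Not Related.

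**4. Does anything later correct the rating?** No. The imputation in SAP Section 13.2.5 applies only where the relationship is missing. The Table 3 limits address statin exposure, not how an event is classified.

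**5. Which outputs depend on the rating, and which do not?**

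- Dependent: the by-relationship TEAE summaries (SAP Section 10.1.1) and the causality entry on SAE reports (Protocol Section 8.3.5).
- Not dependent: TEAE tables by system organ class and preferred term and by severity (SAP Section 10.1.1); SAE reporting to the sponsor, which is required whatever the investigator believes about relationship (Protocol Section 8.1); and summaries of CPK, ALT, AST and bilirubin (SAP Section 10.2).
- The independent checks are weaker for muscle than for liver. SAP Appendix 3 has criteria for ALT, AST and their combination with bilirubin but none for CPK, and the specific adverse events in SAP Appendix 7 include no muscle category.

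**6. Can the number of affected events be estimated?** No. The documents give no rate of statin use and no rate of muscle or liver events.

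**The case against.** The best defence is that the bullets only illustrate. Related takes in any event with evidence of causation by study drug, and rhabdomyolysis is named under Possibly Related, so an investigator who suspects an interaction is free to say so. The interaction is disclosed and statin doses are limited because of it. The safety endpoint is the incidence of TEAEs and TESAEs with no relatedness filter (Protocol Section 3.3), no hypothesis is tested, and the sponsor, not the investigator, reports suspected reactions to authorities. Section 8.2.1 defines an adverse event without any judgement of causality, so it does not contradict the example. Some isolated laboratory rises would not be recorded as adverse events at all (Section 8.3.7) and so would receive no rating.

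Most of this stands, and it limits the reach of the point. A reader might infer that every known co-medication reaction must be rated Not Related and that interaction harm therefore disappears from the related-event tables. The documents do not support that, because the list consists of examples and other categories remain open. A reader might also assume, say, 30% to 60% statin use and conclude that 0.30 × 300 = 90 to 0.60 × 300 = 180 subjects would be misrated. That range is an assumption about statin use, and it counts exposed subjects, not misclassified events.

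The defence does not remove the gap itself. Investigators must follow the guidance, its closest example for a statin-type event points to Not Related without qualification, and for rhabdomyolysis it points both ways.

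**Conclusion.** The point holds as an ambiguity and an omission in the guidance. A statin-type muscle or liver event to which roxadustat may have contributed can be coded Not Related, and rhabdomyolysis in a statin user has two conflicting examples with no precedence. The effect is possible under-attribution, confined to the by-relationship TEAE tables and the investigator's causality input on SAE reports. Overall TEAE incidence, SAE reporting and laboratory summaries are unaffected, with the reservation about CPK noted above.

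The conclusion assumes only that some enrolled subjects take a statin, which the protocol anticipates by setting limits for it. It does not assume that any such event will occur, and its size cannot be stated from the documents. The change is worth making because it costs almost nothing and the study has no comparator to reveal under-attribution.

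**What to change.** In Protocol Section 8.3.4, keep the co-medication example but add a qualifier at its end: *with no reasonable possibility that study drug contributed, including by increasing exposure to that co-medication (see Section 4.7.1.3)*. Then reconcile it with the rhabdomyolysis example, so that the same event in a statin user does not receive two answers.

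Do not add a default that such events are at least Possibly Related unless an interaction is disproved. That would reverse the burden of evidence and conflict with the section's own statement that default reporting as possibly related is uninformative.

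The cost is one amended sentence, the reconciliation and brief site training. A few more events may be rated Possibly Related. No dose, schedule or clinical management rule changes.

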8.3.5. Reporting Serious Adverse Events on the Serious Adverse Event Report Form

All SAEs must be reported immediately to the Sponsor and/or its designated safety management vendor.

To report an SAE, the Investigator must fax or email an SAE Report Form to the Sponsor's designated safety management vendor within 24 hours of becoming aware of the serious event. Follow-up reports must be submitted in a timely manner as additional information becomes available. Full details of the SAE should also be recorded on the medical records and in the CRF. The following minimum information is required:

- Subject number, sex and age
- The date of report
- A description of the SAE (event, seriousness of the event)
- Causal relationship to the study drug

For each SAE observed, the Investigator should obtain all of the information available about the event, including (but not limited to): clinical course of the event, hospital discharge diagnoses, hospital discharge note, death certificate, appropriate laboratory findings (including autopsies and biopsy results), and clinical examinations (including radiological examinations and clinical consultations).

The medical monitor is available to discuss safety issues if needed.

8.3.5.1. Reporting Serious Adverse Events to the Institutional Review Board / Independent Ethics Committee

The Investigator is responsible for notifying his/her Institutional Review Board (IRB) or Ethics Committee (EC) of SAEs in accordance with local regulations. Sponsor, or its safety representative, will provide to the Investigator a copy of any expedited safety reports that it intends to file with a regulatory authority.

